# 6. RECRUITMENT METHODS

Eligible subjects will be identified and recruited in the following ways:

- Subjects with DLE may be recruited from the contact database of Med/AIR Subject Database and Tissue Repository (RSRB#276) or the Evaluation of the Pathogenesis of Cutaneous Lupus Erythematosus study (RSRB#3215) if subjects have previously indicated their interest in being contacted for future studies. The PI of this study ([name]) is also the PI of RSRB#3215 and a sub-investigator on RSRB#276.
- This study will identify potential subjects for recruitment using the UR CTSI Research Participant Registry, STUDY00001978. Subjects enrolled in the URMC Research Participant Registry may be contacted to enroll in this study.
- Subjects may be recruited during routine clinic visits by providers and staff involved in their care. These providers may also include the PI and Sub-investigators. To assist in identifying subjects who have not yet been recruited into this study, the study coordinators may review eRecord charts of individuals prior to their clinic visits to prompt the provider to discuss research with them. Subjects will be approached by staff providing care to obtain the subject's agreement to be contacted by the study team.
- As standard of care, subjects who have been evaluated in the Department of Dermatology or Allergy, Immunology and Rheumatology (AIR) Division, and who have been coded with a lupus specific ICD-9 or ICD-10 code, may have providers reach out and offer for them to be seen in a Dermatology or AIR clinic. They may also be

Version Date: 06Jun2023 Page 7 of 19

offered enrollment in this study. Subjects who do not want to be seen in clinic will still have the option to enroll into this study.

Potential subjects may be contacted via telephone call to discuss the study, field questions and assess interest; an IRB approved Telephone Script will be followed. If the potential subject is interested in participating in the study they will be offered to have the consent form mailed or emailed to them to READ ONLY with an IRB approved Information Sheet with instructions that the consent is for review only. Prior to the consent being mailed or emailed to the potential subject a study team member will cross out the signature page to eliminate confusion. The potential subject will sign a NEW clean consent upon their clinic and/or study visit along with the study team member.

## 7. CONSENT PROCESS

### 7.1 Process of Consent

The consent process will provide information about the study to a prospective participant and will allow adequate time for review and discussion prior to his/her decision. The PI or a qualified study member listed in the CLICK IRB protocol will review the consent form with the participant and answer questions. Consent designees will be listed on the site delegation of responsibilities log, complete consenting certification, and have knowledge of the protocol and study procedures. The PI or designee will meet directly with subjects in a private room and the consent form will be read in its entirety. Any questions will be answered to the subject's satisfaction. The subject's capacity to comprehend the information in the consent form will be assessed by asking questions about the content and encouraging the subject to describe briefly the study procedures. Subjects will be assured that enrollment is voluntary and that they are free to not participate or to withdraw at any time, without risking loss of present or future care that they would otherwise receive. It will be explained to the subject that those who consent to participate in this study will have their contact information and medical history stored in the database. Subjects will be informed that if they withdraw consent, no new information will be collected, and they can choose to have any stored samples discarded. However, data generated from previously used samples may be retained. Subjects will be allowed as much time as necessary to provide consent. Subjects will provide consent by signing the informed consent form for this study. Subjects will receive a signed copy of the consent form. The consent process will be ongoing. The consent form will be revised, and the subjects re-consented, when important new safety information is available, the protocol is amended, and/or new information becomes available that may affect participation in the study.

# 7.2 Consent Forms

Attached in the RSRB application.

# 7.3 Documentation of Consent

Both the study subject and the person obtaining consent will sign and date the consent form in order to document consent.

#### 8. STUDY PROCEDURES

Version Date: 06Jun2023 Page 8 of 19

This study will be a single-arm trial of ruxolitinib 1.5% cream applied twice daily for 12 weeks. Only active lesions will be treated, defined as those with erythema, scale, pain, or pruritus. Each subject will be provided with ruxolitinib cream.

# 8.1 Subject Visits

Each subject will have a total of 7 visits. The initial visit will be the Screening visit, which will occur 7 to 28 days before the start of the trial. Treatment visits will be at weeks 0, 2, 4, 8, and 12, at which times the subject will have assessments performed to document DLE severity and assess safety. A follow-up visit to assess safety will be performed at 16 weeks.

# 8.2 Study Procedures

Clinical assessments, safety procedures, and research procedures will be performed as outlined below per the schedule of activities. In the event that one of these is not able to be completed, disease activity increases or other concerns arise, the subject may be asked to return to the clinic for an "unscheduled visit" to reassess the subject and perform as needed any clinical assessments, safety procedures, or research procedures as outlined below.

### 8.2.1 Clinical Assessments

Clinical Assessments: A detailed physical exam, past medical history and vital signs will be performed at study visit 1. A problem-focused physical exam, interval history and vital signs (heart rate, blood pressure, temperature, weight) will be performed at visits 2-7. Adverse events will be assessed at study visits 2-7.

IGA: The Investigator's Global Assessment will be performed at study visits 2-6. The IGA is an instrument to rate the severity of the subject's global disease. This IGA is comprised of a 5-point scale of disease activity ranging from 0 to 4 as follows:

- 0: "clear," no erythema or scale
- 1: "almost clear," pink erythema without scale
- 2: "mild," pink erythema with scale
- 3: "moderate," red erythema with scale
- 4: "severe," purple/violaceous or hemorrhagic/crusted erythema OR hypertrophic/ verrucous scale

CLASI: The Cutaneous Lupus Area and Severity Index will be performed at study visits 2-6. This is a validated measurement instrument designed for use in clinical trials to assess disease activity and damage in subjects with cutaneous lupus. The CLASI is comprised of two parts, CLASI-A that measures disease activity (erythema and scale), and CLASI-D that measures disease damage (pigmentation and scarring).

NRS: Subjects will maintain a symptom diary every day for 12 weeks. Specifically, subjects will rate pain and itch separately using a numeric rating scale (NRS) and the questions below. Symptom diaries will be reviewed at study visits 2-6.

On a scale of no itch (0) to worst imaginable itch (10), how itchy was the worst discoid

Version Date: 06Jun2023 Page 9 of 19

lupus lesion in the last 24 hours?

On a scale of no pain (0) to worst imaginable pain (10), how painful was the worst discoid lupus lesion in the last 24 hours?

Photography: Photographs of all discoid lesions will be taken at study visits 2-6. The Haiku app or Canto app will be used to directly load photos into the secure Epic medical record system. Images will be extracted from Epic, and analyzed as described. In brief, a melanin index (MI) and an erythema index (EI) will be generated for each lesion using Image J software analysis. The analysis uses perilesional skin to normalize the photograph. Images from serial visits will then be compared, as well as between treatment groups.

Compliance: Tubes of cream will be weighed at each visit. Additional jars/tubes will be supplied as needed at study visits, which will vary depending on the percent body surface area (BSA) involved.

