# 4. STUDY DESIGN

This is a 12-week, single-center, open-label study of ruxolitinib 1.5% cream for the treatment of discoid lupus. The primary endpoint is a ≥ 2-point reduction in Investigator's Global Assessment (IGA) score at Week 12 compared to baseline. Secondary endpoints at Week 12 include the mean percentage change from baseline in the Cutaneous Lupus Erythematosus Disease Area and Severity Index (CLASI), CLASI-A (activity) and CLASI-D (damage) scores; the change in erythema and pigmentation as determined by quantitative photographic analysis; and the change in numeric rating scale (NRS) for pain and pruritus. Exploratory endpoints of skin biopsies will evaluate cellular and molecular features of discoid lesions preand post-treatment for 1) predictors of treatment response, and 2) treatment response to ruxolitinib. Quantitative and qualitative measures of the cutaneous inflammatory response, including evaluation of the immune cell infiltrate and IFN signature, will be assessed.

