# 17. DATA ANALYSIS PLAN

This exploratory study has a sample size of 15 subjects. Given the small sample size, a robust statistical analysis will be limited. The primary endpoint will be a  $\geq$  2-point reduction in IGA score. The mean percentage change from baseline will be assessed for the secondary endpoints (CLASI, CLASI-A, CLASI-D, NRS, EI, MI). Statistical analysis of exploratory endpoints comparing skin tissue before and after ruxolitinib treatment will be performed in accordance with the technique being used (histology, flow cytometry, RNAseq). Analyses of DLE histology (H&E, IHC, IFM) will include common histologic features (follicular plugging, interface change, etc.), cell counts of the immune infiltrate, and markers of IFN response. Flow cytometric analysis will evaluate the immune infiltrate, including T and B cell subsets. The focus of the RNAseq analysis will be on interferon expression, though other analyses may be performed. Differences will be considered significant at p < 0.05.

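### The 12-week NRS diary has no stated start: begun at Visit 2 it gives at most one pre-treatment entry, and begun at screening it stops before Week 12

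*Combined protocol and SAP*

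**What the plan says.** Pain and itch are collected only by a subject diary. Section 8.2.1 states "Subjects will maintain a symptom diary every day for 12 weeks" and "Symptom diaries will be reviewed at study visits 2-6". Each item asks the subject to score, from 0 to 10, the worst discoid "lupus lesion in the last 24 hours".

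On timing, Section 8.1 states "The initial visit will be the Screening visit, which will occur 7 to 28 days before the start of the trial" and "Treatment visits will be at weeks 0, 2, 4, 8, and 12". Section 8 describes a "single-arm trial of ruxolitinib 1.5% cream applied twice daily for 12 weeks", so the diary and the treatment period have the same nominal length. The schedule in Section 8.2.4 marks diary review at Visit 2 (day 0) and at every later visit through Visit 6, but nothing for the diary at screening. Visit 6 is day 84 with a window of 3 days either side.

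On analysis, Section 4 lists "the change in numeric rating scale (NRS) for pain and pruritus" among the Week 12 secondary endpoints. Sections 8.2.5 and 17 make it a mean percentage change from baseline. No section says when the diary is issued, when the first entry is made, which entries are the NRS baseline, or which entries are the Week 12 value.

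**The concern.** A change-from-baseline endpoint needs data on both sides: something before treatment and something at Week 12. A diary as long as the treatment period, with no start date, does not clearly supply both. Review at Visit 2 implies that something has been written by then, yet the stated length leaves no room for a pre-treatment period if the diary is also to reach Week 12.

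Baseline matters more than usual here because it is the denominator of a percentage. Eligibility (Section 5.1) sets no minimum pain or itch score, so a single day's recall can be very low or zero, and the percentage change is then unstable or undefined. With 15 subjects and no control arm, a few such values can dominate a mean. Since the entries are not specified, someone must choose them later, with open-label data in view.

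Biopsy adds a complication. In consenting subjects a discoid lesion is punched at Visit 2 (Section 8.2.3), and the diary asks about the worst lesion. Entries in the following days could reflect the procedure.

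**Working it through.** **Inputs.** Diary length 12 weeks and 24-hour recall (Section 8.2.1); screening on day -28 to -7 (Section 8.1); Visit 2 on day 0, and Visit 6 on day 84 with a window of days 81 to 87 (Section 8.2.4).

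**Step 1: diary length.** 12 × 7 = 84 daily entries. This matches the treatment period from day 0 to day 84.

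**Step 2: where 84 entries end.** Last entry = first day + 83.

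| First entry | Last entry | Entries before day 0 | Days short of day 84 |
|---|---|---|---|
| Day -28 | Day 55 | 28 | 29 |
| Day -7 | Day 76 | 7 | 8 |
| Day 0 | Day 83 | 0 | 1 |
| Day 1 | Day 84 | 0 | 0 |

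Counting elapsed days instead moves the screening-start results by one day: 84 − 28 = 56 and 84 − 7 = 77. In the day 0 row, the day 0 entry itself describes the 24 hours before treatment, provided it is made before the first application.

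**Step 3: does the visit window rescue it?** The earliest Visit 6 is day 81. A diary begun at the latest permitted screening ends on day 76, which is 81 − 76 = 5 days too early. Visit 1 to Visit 6 spans 7 + 84 = 91 to 28 + 84 = 112 days at nominal timing, or 7 + 81 = 88 to 28 + 87 = 115 days with the window. Against 84 diary days, the shortfall is 7 to 28 days nominally and 4 to 31 days with the window. Working back from a day 81 visit, the first of 84 entries falls on 81 − 83 = day -2, giving two entries before day 0; but no visit or instruction sets such a start.

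**Step 4: what full coverage needs.** Daily entries from screening through day 84 inclusive number 7 + 84 + 1 = 92 to 28 + 84 + 1 = 113.

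**Step 5: one entry or a 7-day mean (assumed correlations).** If any two days within a subject correlate at r, the ratio of the baseline SD with a 7-day mean to that with one entry is √((1 + 6r)/7).

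- r = 0.4: √(3.4/7) = 0.70, a 30% reduction
- r = 0.6: √(4.6/7) = 0.81, a 19% reduction
- r = 0.75: √(5.5/7) = 0.89, an 11% reduction

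The documents give no value of r. These figures describe the spread of the baseline, not of the percentage change.

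**Step 6: what the wrong days could do (assumed scores).** Suppose true pre-treatment itch is 6, the first on-drug week averages 4, and Week 12 is 2. The change is (6 − 2)/6 = 67% from the true baseline but (4 − 2)/4 = 50% from the on-drug one. Conversely, if soreness after biopsy lifts the first week to 7, a subject who stays at 6 throughout shows (7 − 6)/7 = 14% improvement. Both cases require post-Visit 2 days to be used as baseline.

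**The case against.** The strongest reply is that a baseline does exist. The schedule places diary review at Visit 2 alongside IGA, CLASI and photography. With a 24-hour recall, an entry completed there before application and biopsy is wholly pre-treatment and gives the NRS the same single-visit baseline as those measures. This stands. A reader might infer from the 84-day length that there is no pre-treatment baseline at all; the Visit 2 review does not support that.

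A reader might also infer a definite bias, towards or away from benefit. The documents do not support this either. It needs on-treatment or post-biopsy days as baseline, and no section says they will be used. Biopsies are optional with uptake not given, and the scores in Step 6 are invented for illustration.

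It can further be said that 12 weeks is a loose label for the treatment period rather than a count of 84 entries. That is plausible, but it leaves the start and both analysis windows undefined.

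Finally, a 7-day run-in is not free of problems. Section 5.2 excludes topical lupus treatments within 2 weeks of Visit 2, and Section 9.1 accepts that stopping them may worsen disease, so symptoms may be drifting during that week. At the 7-day minimum interval, seven entries are obtained only if the diary starts at once and none is missed. Both points are fair. The first applies to the single Visit 2 entry as well, since that also falls in the off-topical period. The second calls for a minimum-entry rule.

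**Conclusion.** The point holds as a gap in the collection and definition of a secondary endpoint. Read literally, 84 daily entries cannot cover the screening interval and also reach Week 12. A screening start loses the Week 12 value by at least 5 days against the earliest visit; a Visit 2 start leaves at most one pre-treatment entry. The calendar result rests only on the protocol's own dates. The precision gain from averaging is an assumption-based range, 11% to 30% of baseline SD for correlations of 0.75 down to 0.4.

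The single Visit 2 entry is usable but noisy, and bias remains a possibility that the plan leaves open. The IGA primary endpoint is untouched. Section 17 already concedes that robust analysis will be limited, so this is a cheap improvement rather than a threat to the study's main result.

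**What to change.** In Section 8.2.1 and the schedule in Section 8.2.4, hand out the diary at Visit 1 and have it kept daily through Visit 6, in place of the fixed 12-week length. In Sections 8.2.5 and 17, define:

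- **Baseline NRS**, separately for pain and itch: the mean of the available entries in the 7 days before the first Visit 2 application and any Visit 2 biopsy.
- **Week 12 NRS**: the mean of the available entries in the 7 days before Visit 6 and its biopsy.
- **Minimum data**: a stated number of entries in each window, for example 4 of 7.

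The minimum screening interval of 7 days makes the baseline window possible for every subject, and that window lies inside the existing off-topical period.

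The cost is 7 to 28 more days of a two-question diary per subject, compared with a diary kept from Visit 2 to Visit 6, and no extra visit. The protocol and consent wording must be updated, and Section 7.1 calls for re-consent when the protocol is amended. If the diary is not extended, the least that is needed is to state that the first entry is made at Visit 2 before application and biopsy, to name it as the baseline, and to define the Week 12 window.

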# 8.2.2 Safety Monitoring

History & Exam: An interval history and problem focused physical exam will be performed at each visit. Subjects will also be asked about recent systemic infections. The focused exam will also include an assessment of the skin immediately surrounding the DLE lesion for irritation using a standard 8-pt scale. This scale was developed by Berger and Bowman to assess the effect of topicals on normal skin; any visual assessment methodology for irritation on an already inflamed DLE lesion would not be informative.

Phlebotomy: Blood draws will be performed by a trained phlebotomist. A complete blood count (CBC), comprehensive metabolic panel (CMP), and lipid panel will be assessed at the screening visit. Additional labs will be drawn as follows: CBC and CMP at 4 and 12 weeks, lipid panel at 12 weeks. Standard of care laboratories may be drawn at the same time for subject convenience. The venipuncture site will be covered with gauze and a bandaid.

Urine pregnancy test: Urine pregnancy tests will be performed at screening and monthly during treatment for all females of childbearing potential. Menopause is defined as at least 12 consecutive months without menses; if in question, a follicle stimulating hormone of ≥25 U/mL must be documented. Hysterectomy, bilateral oophorectomy, or bilateral tubal ligation must be documented, as applicable; if documented, a urine pregnancy test is not required for women with these conditions.

### 8.2.3 Research Procedures

Optional skin biopsies at weeks 0 and 12 will be analyzed as follows:

- Histology: H&E, immunohistochemistry (IHC), and/or immunofluorescence microscopy (IFM)
- Flow cytometry/cell sorting: composition of inflammatory infiltrate
- RNAseq: IFN signature

Version Date: 06Jun2023 Page 10 of 19

Biopsy: For subjects that are willing to provide an optional skin biopsy, two discoid lesions with equal IGA scores (3 or 4) will be selected at Visit 2, one of which will be biopsied at that visit. At visit 6, the other lesion will be biopsied.

After obtaining informed consent, a skin biopsy will be obtained by a study practitioner trained in this procedure. A biopsy will consist of removing a piece of skin with a 4-mm skin biopsy punch. The biopsy will be performed after injecting a local anesthetic (lidocaine with epinephrine) to minimize pain and blood loss. At the biopsy site one or two sutures may be placed to improve healing, reduce blood loss and scar formation. A pressure bandage will be applied to the biopsy site to minimize the risk of bleeding and infection. The biopsy will be divided as appropriate for subsequent analysis.

All study subjects will be given the option to visit the study center for suture removal 7-14 days after the biopsy was taken. Our experience is that some of our study subjects, especially the ones who live far from the study center, prefer to have their sutures removed by a local physician, health care provider, family member or friend trained on removing sutures. Nevertheless, we will strongly recommend in each case that the study subject return to the study center for removal of suture so that we can evaluate whether the biopsy site is healing well.

We will provide each subject with a wound care instruction sheet which says:

"If non-absorbable stitches were placed, they should be removed either by returning to the University of Rochester Department of Dermatology or by a local physician, health care provider, family member or friend with experience removing sutures in 7 to 10 days from their placement. If possible, keep the biopsy site completely dry for the first 24 hours after the biopsy. After that, change the band-aid and apply petroleum jelly to the site on a daily basis. We have provided you with the supplies to do this. The site will appear a bit red and may be itchy after several days and that is a normal healing response. Please contact us if at the site of the skin biopsy the pain increases, the dressing continues to be saturated with blood or there is foul-smelling, pus-like drainage from the site (after the first 2 days). For any questions or concerns, or to arrange for stitch removal, call the Clinical Coordinators - at [contact] or [contact]."

Histology: We will analyze the DLE skin tissue using IHC and/or IFM. Common features of DLE histology will be evaluated, including hyperkeratosis, epidermal atrophy, follicular plugging, interface change, and immunoglobulin deposition. A quantitative analysis of immune cell counts will be performed. Markers of IFN response will be analyzed.

Flow Cytometry: We will evaluate the immune and other cell types from disaggregated DLE skin tissue by multi-color flow cytometry per lab protocols.

Transcriptomics: The IFN signature will be evaluated by RNAseq.

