#### 1. PURPOSE OF STUDY

The primary objective of this study is to assess the potential efficacy of topical ruxolitinib for the treatment of discoid lupus erythematosus (DLE). We propose a 12-week open-label clinical trial. An exploratory objective of this study is to analyze cellular and molecular features of discoid lesions before and after treatment with topical ruxolitinib to assess 1) predictors of treatment response, and 2) treatment response to ruxolitinib.

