# 5. INCLUSION AND EXCLUSION CRITERIA

#### 5.1 Inclusion Criteria

# Individuals who meet all of the following criteria are eligible for enrollment as study participants:

- Ability to understand and comply with the protocol and provide informed consent.
- Speaks English.
- Age  $\geq$  18 years.
- Clinical diagnosis of discoid lupus as assessed by the PI.
- At least one active (inflamed) discoid lesion with an IGA score of  $\geq 3$  and with a diameter  $\geq 1$  cm at screening and baseline. Two lesions with equal scores will be necessary if consenting to pre-and post-treatment biopsies.
- Maximum body surface area of 20%.

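### The tissue comparison pairs two different lesions with no rule for which is biopsied first, and the lesion punched at Visit 2 is not excepted from EI and MI; both are cheap to tidy.

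*Combined protocol and SAP*

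**What the plan says.** All references are to the combined protocol and SAP.

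- **Lesion choice.** Section 5.1 sets one matching condition: "Two lesions with equal scores will be necessary if consenting to pre-and post-treatment biopsies". Section 8.2.3 repeats it: "two discoid lesions with equal IGA scores (3 or 4) will be selected at Visit 2, one of which will be biopsied" at that visit. Then: "At visit 6, the other lesion will be biopsied". Neither section says who picks the first lesion or on what basis.
- **Analysis of the pair.** Section 17: "Statistical analysis of exploratory endpoints comparing skin tissue before and after ruxolitinib treatment will be performed in accordance with the technique being used". It adds: "Differences will be considered significant at p < 0.05". It does not mention that the two samples come from different lesions.
- **Purpose of the tissue work.** Section 1 makes it exploratory, with two aims: "predictors of treatment response, and 2) treatment response to ruxolitinib".
- **Photographic endpoints.** Section 8.2.1: "Photographs of all discoid lesions will be taken at study visits 2-6", and "a melanin index (MI) and an erythema index (EI) will be generated for each lesion". Sections 8.2.5 and 17 make EI and MI secondary endpoints, analysed as mean percentage change from baseline. No section sets aside the lesion punched at Visit 2.
- **Biopsy marks.** Section 8.2.3 specifies a 4-mm punch. Its wound-care text expects some redness in early healing. Section 9.1 lists a scar and a low risk of discoloration.

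**The concern.** A before-and-after contrast normally samples the same unit twice. Here the baseline sample comes from one lesion and the week-12 sample from another, so the difference contains the drug effect, change over time, and any pre-existing difference between the lesions. The last part averages to zero only if the order of biopsy is unrelated to the tissue markers.

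Equal IGA gives partial matching. The score grades erythema and scale; it does not grade the immune infiltrate or interferon signature that the biopsies measure. Grade 4 is also broad: it is met by either severe erythema or hypertrophic scale, so two grade-4 lesions can look quite different. If the more inflamed lesion tended to be taken first, the pair would show a fall with no drug effect; the reverse habit would hide a real one. Only the treatment-response aim is exposed, because predictors of response rest on the baseline sample alone.

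The second issue is separate. A lasting mark that the study itself makes in one lesion would be counted as change on treatment in EI and MI.

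**Working it through.** The plan gives no power or sample-size calculation for the tissue comparison or for EI and MI, so there is no figure to reproduce. What follows is illustration.

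**1. Lesion choice**

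From the documents: 15 subjects (Sections 4.1.1 and 17), optional biopsy with no stated uptake, significance at 0.05, no named test.

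Assumed: 10 pairs; a two-sided paired t-test; no drug effect and no change over time; two lesions per subject with independent standard-normal marker values; the visually worse lesion taken first with probability q; ρ, the correlation between visual severity beyond IGA and the marker.

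Expected false change, in lesion SDs: −(2q − 1) × ρ × 2/√π, where 2/√π = 1.128.

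- q = 0.5: 0
- q = 0.7, ρ = 0.4: −0.4 × 0.4 × 1.128 = −0.18
- q = 0.7, ρ = 0.6: −0.4 × 0.6 × 1.128 = −0.27
- q = 0.8, ρ = 0.6: −0.6 × 0.6 × 1.128 = −0.41

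Simulated false-positive rates, 10 pairs:

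| Worse lesion first (q) | ρ = 0.4, assay variance equal to lesion variance | ρ = 0.6, no assay error |
|---|---|---|
| 50% (random) | 5.0% | 5.0% |
| 60% | 5.1% | 5.9% |
| 70% | 5.7% | 8.7% |
| 80% | 6.6% | 13.9% |

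Repeating the simulation with other seeds moves these by at most about 0.3 percentage points. With 5 pairs, the 70–80% settings run from 5.2% to 8.6%; with 15 pairs, from 6.2% to 19.5%. The extreme case, ρ = 1 with no assay error, gives 19% and 39% at 10 pairs for q = 0.7 and 0.8, but it requires the eye to rank the tissue marker perfectly.

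For scale: with random choice and 10 pairs, a natural fall over 12 weeks of 0.25 or 0.5 lesion SD (no assay error) gives rejection rates of 7.9% and 17.0%. Random choice does not remove this single-arm limit.

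**2. Biopsy mark in EI and MI**

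From the documents: 4-mm punch; minimum eligible lesion diameter 1 cm (Section 5.1); 15 subjects.

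Assumed: the mark stays within the punch, EI and MI are averaged over the lesion area, lesions count equally within a subject, 10 of 15 subjects are biopsied, two lesions each.

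- Share of lesion area: (4/10)² = 16% at 10 mm; (4/20)² = 4% at 20 mm.
- Weight of the biopsied lesions in the trial mean: (10/15) × (1/2) = 33%.
- Share of the local colour shift reaching the trial mean: 0.333 × 0.16 = 5.3% at 10 mm; 0.333 × 0.04 = 1.3% at 20 mm.

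The size of the local shift itself cannot be derived from the documents.

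**The case against.** The two-lesion design is deliberate and disclosed in Sections 5.1 and 8.2.3. It avoids sampling the scar of the first punch and is defensible. Nothing here argues against it.

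A reader might infer that staff pick the first lesion by eye. The documents do not say so: Section 8.2.3 is silent on who chooses and how. Bias needs a choice that consistently follows inflammation beyond IGA, and the 60–80% tilt has no basis in the text. At the low end the inflation is negligible, and the assumed natural fall of 0.5 SD does more harm than any setting in the table. This objection stands as to size. It does not supply the missing rule, and the choice cannot be remade once the punch is taken. Visit 2 photographs would allow a later adjustment, but none is planned, and it would correct only what a photograph shows.

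The tissue aims are exploratory, and Section 17 concedes that robust analysis will be limited. That caveat concerns sample size, not different lesions, and the significance threshold remains.

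That the punched lesion stays in EI and MI is an inference from the wording about all lesions and each lesion. Section 8.2.1 summarises the image method only briefly and does not say which region is measured or how lesions combine. Inclusion is the natural reading, but not an explicit statement. The redness described belongs to early healing, so at Week 12 discoloration or scar is the likelier residue.

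A reader might also infer that the whole 33% weight of the biopsied lesions carries the mark. It would not if the mark is confined to a 4-mm site in a larger lesion. Nor do the documents support saying that biopsy scars will inflate CLASI-D: Section 8.2.1 defines that score as damage from the disease, which a biopsy scar is not.

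**Conclusion.** The point holds as a cheap improvement, not as a flaw that undermines the trial. The text establishes three facts: two different lesions matched only on IGA score, no rule for which is biopsied first, and no stated exception for the punched lesion in EI and MI.

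The consequence for the tissue comparison is conditional on selective choice, unknown in direction and modest at moderate correlations. It rests on the assumed tilt, correlation, number of pairs and t-test. The EI and MI effect is probably small and rests on area averaging, equal lesion weights and assumed biopsy uptake. Both issues are confined to subjects who accept the optional biopsy, and the primary IGA endpoint is not affected.

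**What to change.** 1. **Section 8.2.3.** Once both lesions are judged suitable for biopsy, take the Visit 2 lesion from a random list prepared in advance, and record which it was. This removes only the lesion-choice bias.
2. **Sections 8.2.1 and 17.** Report EI and MI change with and without the lesion biopsied at Visit 2. The second version loses one lesion per biopsied subject, half the data where there are only two; reporting both keeps the full data in view.
3. **Section 17.** Describe the tissue result as a comparison between matched lesions which, in a single arm, cannot separate drug effect from change over time. Random choice does not cure this, so the wording is needed as well.
4. **Minor clarification, Section 8.2.1.** Remind raters that a biopsy scar is not disease damage for CLASI-D.

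The cost is a short list, a few sentences and one extra analysis, with no additional biopsy, visit or staff. The list must be in place before a subject's Visit 2.
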